A meta-analysis by Xing TF, *et al* involving 10 randomized controlled trials suggested that routine post-operative calcium and vitamin D supplementation significantly reduced the rate of hypocalcaemia and the demand for intravenous calcium supplementation as compared to either no treatment or calcium alone^{5,12}. While there is evidence regarding the role of post-operative supplementation, there is little

literature reporting on the role of routine pre- and post-total thyroidectomy calcium and vitamin D supplementation in preventing post-operative hypocalcaemia. Routine pre- and post-total thyroidectomy calcium and vitamin D supplementation have been shown to reduce the rate of post-operative hypocalcaemia and length of hospital stay^{6,7}.

Interestingly, there was a randomized controlled trial performed by Besic, *et al* who studied whether magnesium infusion prior to total thyroidectomy will influence the onset of transient hypocalcaemia. This is as normomagnesaemia is needed for the normal secretion of parathyroid hormone. However, no statistical difference was identified between the intervention and control groups^{9,12}. It is essential to measure serum magnesium in any patient who is hypocalcaemic, as the correction of hypomagnesaemia must occur to overcome parathyroid hormone (PTH) resistance before serum calcium can be normalised with calcium supplementation¹⁴.

Pre-operative parathyroid hormone level can help to predict and anticipate post-operative hypocalcaemia. If the pre-operative PTH is less than 4.7pmol/L, the risk of developing transient hypoparathyroidism is 2.4 times higher than the normal population and thus there is a higher risk of developing post-operative hypocalcaemia¹⁰. Pre-operative calcium levels can also help to predict post-operative hypocalcaemia. A retrospective study by Amir, *et al* found that corrected pre-operative serum calcium levels of less than 2.27 mmol/L was associated with a 63% chance of developing post-thyroidectomy hypocalcaemia whereas those with calcium levels above 2.27 mmol/L have a 24% chance of developing hypocalcaemia¹¹.

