Patient will be recruited from the endocrine surgery outpatient clinic and in-patient referrals for total thyroidectomy. There are several inclusion and exclusion criteria for recruitment into this study. After fulfilling the inclusion criteria, patients will be required to give consent and agree to participate in this study after explanation by the clinician and investigator in charge. Participants will be randomized into an intervention group (Group A) and a control group (Group B) with the ratio of 1:1 during admission for surgery (**Appendix 2**). The method of randomization utilised will be random randomization. Both the surgeon and patient will not be aware of the randomization arm of any particular patient. Only the primary investigator and assistants will be aware of the randomization of a patient. Before surgery, baseline serum calcium, magnesium and i-PTH will be obtained. If intra-operatively, all 4 parathyroid glands are accidentally removed during the total thyroidectomy, these patients will be excluded from the study as this will definitely affect their serum calcium levels post-surgery.

After total thyroidectomy, the intervention group will receive a calcium gluconate infusion over one hour (1g of intravenous calcium gluconate, diluted in 100mls of normal saline) within 4 hours after skin closure. On the other hand, the control group will receive a saline infusion (100 ml of normal saline) infused over one hour within 4 hours of skin closure. Both groups will be put on cardiac monitoring

during the administration of the intravenous infusion. The dosing, dilution and infusion rate for the calcium gluconate are within the safety limits as recommended by FDA and WHO model formularies.

Post-total thyroidectomy, both groups of patients will receive the same regime of oral calcium carbonate 1g t.d.s. and oral Rocaltrol 0.25mcg o.d. as per current protocol in the endocrine surgery unit. Serum calcium levels will be obtained at the 6-hour, 12-hour, 36-hour, 48-hour mark post-surgery. The blood samples collected will be sent to the biochemical laboratory of UMMC.

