In the endocrine surgery unit, the current practice is that all patients who had total thyroidectomy performed will be kept as an in-patient routinely for at least 48 hours so that their serum calcium levels can be monitored at the intervals mentioned above (6-hour, 12-hour, 24-hour, 36-hour & 48-hour). Therefore, this study will not incur an additional stay or prolonged admission.

Target Population

The target population is from the endocrine surgery clinic and UMMC ward. Target population consists of all patients scheduled for total thyroidectomy during the period of 1st June 2020 to 31st May 2022.

Sample Size

A pilot study will be conducted after obtaining approval from MREC (Medical Research Ethics Committee) UMMC. 10 patients will be recruited for the pilot study and randomized into 5 patients each arm. Sample size calculation will then be derived from the mean and standard deviation obtained from the pilot study.

Inclusion Criteria

- Age between 18-80 years old
- Scheduled for total thyroidectomy in UMMC

Exclusion Criteria

- Their age outside the range of 18-80
- Have parathyroid disorders or end stage renal failure
- On calcium or vitamin D supplements prior to surgery
- Have deranged calcium homeostasis pre-operatively (outside the normal range of 2.2-2.6 mmol/L)
- Scheduled for total thyroidectomy plus lymph node dissection

Withdrawal Criteria

Subjects can choose to withdraw at any time and withdrawn subjects will not be replaced.

Study Duration and Time-line (refer to Gantt Chart)

The total research period is from October 2019 till February 2023. The first two months will be spent on literature review of the relevant papers and the next two months will be on preparation of the research proposal. Subsequently, the research proposal will be submitted to MREC for approval.

After the proposal is approved by MREC, data collection will tentatively start from June 2020 till May 2022. Subsequently, data analysis will start from June 2022 till October 2022. Another two months will be spent on the final report writing and finally thesis presentation and submission on January to February 2023. (please refer to the Gantt chart)

Data Collection Tools and Techniques

As this is a prospective randomized controlled trial, relevant participants information and blood investigations will be recorded and documented in the Electronic Medical Record (EMR). These data will then be transcribed into SPSS for analysis.

Data Analysis

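### The randomisation method is not defined: it does not guarantee the 5:5 pilot, and it leaves unused a baseline calcium predictor that the protocol itself cites

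*Protocol*

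**What the plan says.** Under Study Type and Design, the protocol allocates patients to two groups "with the ratio of 1:1 during admission for surgery" and then gives the method: "The method of randomization utilised will be random randomization". It mentions no block, stratum or minimisation factor, and it does not call the method simple or unrestricted. The ratio sentence points to Appendix 2, whose content is not in the text available.

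Under Sample Size: "10 patients will be recruited for the pilot study and randomized into 5 patients each arm". The main trial has no stated size: "Sample size calculation will then be derived from the mean and standard deviation obtained from the pilot study".

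The Literature Review reports, from a retrospective study, that "corrected pre-operative serum calcium levels of less than 2.27 mmol/L was associated with a 63% chance of developing post-thyroidectomy hypocalcaemia", while patients with "calcium levels above 2.27 mmol/L have a 24% chance of developing hypocalcaemia". The exclusion criteria remove patients who "Have deranged calcium homeostasis pre-operatively (outside the normal range of 2.2-2.6 mmol/L"). The 2.27 cut-off therefore lies inside the eligible range. Baseline calcium is measured before surgery in every patient.

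Data Analysis names a paired t-test, a Student's t-test between groups and a chi-square test. It names no baseline covariate.

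**The concern.** Two things look wrong.

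First, the method sentence is circular. Nobody could build or audit an allocation list from it. Its most natural reading, simple randomisation, sits badly with a pilot whose arms are fixed at 5 and 5. The pilot's mean and standard deviation are to set the size of the main trial, so its split has some consequence.

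Second, the protocol identifies a predictor that, on its own citation, separates a 63% from a 24% risk. Eligible patients can fall on both sides of the cut-off. The value is already needed to confirm eligibility, and the study endpoint is itself a calcium level. Even so, nothing in the stated allocation or the named tests uses it. At stake are the precision of the comparison and how convincing the result looks if one arm happens to hold more low-calcium patients.

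**Working it through.** **1. Pilot split.** The only allocation figure in the plan is 5:5, which is simply 10 patients divided 1:1. Under simple randomisation:

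- P(exactly 5:5) = C(10,5)/2^10 = 252/1024 = 24.6%.
- P(7:3 or more uneven) = 2 × (1 + 10 + 45 + 120)/1024 = 352/1024 = 34.4%.
- Relative to 5:5, the standard error of a mean difference at 3:7 is √[(1/3 + 1/7)/(2/5)] = 1.09, a 9% increase.

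**2. Inputs for the baseline-calcium question.**

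- Risks of 0.63 and 0.24, from the Literature Review; gap 0.39.
- Share q of patients below 2.27 mmol/L: not in the protocol. Assumed 0.3, range 0.2-0.4.
- Total N: not in the protocol. Assumed 40 (the size of the randomised trial cited in the Literature Review) and 100.
- Equal arms, no treatment effect.

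**3. Formulas.**

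- Overall rate m = 0.63q + 0.24(1−q).
- Total variance V = m(1−m).
- Part due to the stratum B = q(1−q) × 0.39².
- SE of the rate difference ignoring the stratum = √(4V/N); using it = √(4(V−B)/N).
- Relative reduction = 1 − √(1 − B/V), which does not depend on N.

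**4. Worked case, q = 0.3.**

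- m = 0.189 + 0.168 = 0.357; V = 0.357 × 0.643 = 0.2296.
- B = 0.21 × 0.1521 = 0.0319; B/V = 13.9%.
- N = 40: √(4 × 0.2296/40) = 15.2 points; √(4 × 0.1976/40) = 14.1 points.
- Reduction = 1 − √0.861 = 7.2%.

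| q | m | B/V | SE at N=40, before → after | SE at N=100, before → after | Reduction |
|---|---|---|---|---|---|
| 0.2 | 0.318 | 11.2% | 14.7 → 13.9 | 9.3 → 8.8 | 5.8% |
| 0.3 | 0.357 | 13.9% | 15.2 → 14.1 | 9.6 → 8.9 | 7.2% |
| 0.4 | 0.396 | 15.3% | 15.5 → 14.2 | 9.8 → 9.0 | 7.9% |

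**5. Size of the chance shift.** The SD of the shift in the rate difference caused by stratum imbalance is √(4B/N). At q = 0.3 this is 5.7 points at N = 40 and 3.6 points at N = 100. It must be read against the total standard errors of 15.2 and 9.6 points, of which it is already a component.

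**6. Sensitivity to the borrowed gap.** B grows with the square of the gap. If the gap among eligible patients were half the cited one (0.195, with m unchanged), B/V at q = 0.3 would be 13.9%/4 = 3.5% and the reduction only 1.8%.

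**7. Does stratified blocking settle the pilot?** Not alone, because each stratum can stop mid-block. In a simulation of 10 patients with two strata, q = 0.2-0.4 and block sizes drawn at random from {2,4}, {4,6} or {2,4,6}, the overall split was exactly 5:5 in about 54-65% of runs. A single block of 10 gives 5:5 with certainty.

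**The case against.** The strongest reply is that the text never says the allocation is unrestricted. The fixed pilot split fits a restricted scheme that was badly described at least as well, and Appendix 2 may hold the detail. This stands as far as it goes: simple randomisation is an inference, and missing operational detail is not counted here. It does not rescue the sentence in the body, which names no method on either reading.

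A reader might infer that the stated method cannot produce 5:5. It can, about one time in four; the most that can be said is that the split is not assured.

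A reader might also infer that chance imbalance in calcium biases the comparison, or that the planned tests are invalid because they leave it uncorrected. The documents do not support that. Over repeated randomisations the imbalance averages to zero, and the standard errors of the unadjusted tests already contain it. Nor can the shift be called comparable to the treatment effect, since the protocol states no target effect.

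Two further limits stand. The 63% and 24% come from a retrospective study that the protocol does not describe as confined to 2.2-2.6 mmol/L. Its low group may include patients below 2.2, whom this trial excludes. And the main trial's size is unknown, so calling it small is an assumption.

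Finally, baseline adjustment gives most of the same gain without stratifying and is often left to an SAP, which is not at hand. Its absence is therefore not counted as an omission. The point is that the method and tests the protocol does state make no use of a predictor it has already identified and measures anyway.

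**Conclusion.** The concern holds in a limited form. The allocation sentence defines no method and needs replacing. Read as simple randomisation, it meets the pilot's 5:5 only 24.6% of the time. Using baseline calcium in the allocation and the analysis would be a modest improvement: about 6-8% off the standard error of the rate difference at the cited risks with 20-40% of patients below 2.27 mmol/L, and under 2% at q = 0.3 if the gap among eligible patients is half the cited one. No figure can be given for the calcium level itself, because the documents do not give its correlation with baseline. There is no bias and no inflation of type I error. The change is worth making because it is nearly free, not because the trial would otherwise be invalid.

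**What to change.** Replace the method sentence with: computer-generated permuted blocks, 1:1, of undisclosed varying size, stratified by pre-operative corrected calcium (below 2.27 mmol/L versus 2.27 or above).

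Adjust the between-arm analysis to match: ANCOVA with continuous baseline calcium for the calcium level, and a stratified or logistic analysis for the hypocalcaemia rate. Continuous baseline calcium is the better covariate; the stratum is the minimum. Without this step an unadjusted test keeps the larger standard error and much of the gain is lost.

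For the pilot, either allocate its 10 patients in one block of 10 or change Sample Size to say about 5 per arm.

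The cost is two allocation lists instead of one and a few protocol sentences, with no new measurement. There are two small downsides. The calcium result must be looked up at allocation, which the eligibility check already requires. Blocks also make later assignments somewhat more predictable to staff who know earlier ones, and under this protocol the primary investigator and assistants do. Varying, undisclosed block sizes limit this; the single pilot block of 10 is more exposed, which favours rewording the pilot split if that matters.

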Secondary Objectives

- To determine whether prophylactic infusion of calcium gluconate reduces the length of hospital stay as compared to placebo group

Study Endpoint

- The level of corrected calcium in the first 48 hours after total thyroidectomy between intervention and control group

Hypothesis

- Null hypothesis: prophylactic infusion of calcium gluconate does not reduce post-total thyroidectomy hypocalcaemia and length of hospital stay as compared to placebo group
- Alternative hypothesis: Prophylactic infusion of calcium gluconate reduces the rate of post-total thyroidectomy hypocalcaemia in the first 48 hours and shorten the length of hospital stay as compared to placebo group

Methodology

Current Protocol in UMMC

All patients admitted or scheduled for total thyroidectomy in UMMC will have their baseline serum calcium and i-PTH levels checked one day before surgery. Subsequently, all patients will have their serum calcium levels checked at the 6-hour, 12-hour, 24-hour, 36-hour and 48-hour mark post-surgery. The i-PTH level will be tested at the 12-hour post-surgery mark together with the serum calcium level. Oral calcium supplements 2g a day (Calcium Carbonate 1g b.d.) and Rocaltrol 0.25mcg o.d. will be started once the patients are able to tolerate orally. If a patient experiences symptoms of hypocalcaemia and the serum calcium level is less than 2.0mmol/L, the patient will be administered a rescue dose of intravenous calcium gluconate (3g of calcium gluconate in 50mls of normal saline) over 4 hours duration. However, if a patient experiences hypocalcaemia symptoms and the serum calcium level is more than 2.0mmol/L, the patient will be continued on oral supplements at an increased dosage (3-4g of calcium carbonate a day). The usual hospital stay for a total thyroidectomy patient is 48 hours post-surgery. If a patient is asymptomatic and the serum calcium level is normal at 48-hours post-surgery, the patient can be discharged with an appointment at the outpatient clinic in two weeks time.

Study Type and Design

This is a single centre, double blinded and prospective randomized controlled trial which will be conducted in University Malaya Medical Centre (UMMC), Endocrine Surgery Unit. The duration of the study will be from June 2020 until May 2022 (2 years duration).

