During blood taking and review, the patient will be assessed for symptoms of hypocalcaemia such as perioral numbness, spasm, etc. During assessment, if there are clinically suggestive symptoms of hypocalcaemia, the symptoms will be classified into mild or severe symptoms (**Appendix 1**). If a patient exhibited signs of mild hypocalcaemia like perioral numbness, limbs numbness and positive Chvostek's sign, then immediate biochemical investigations including corrected serum calcium level will be performed and the results traced. If the results show serum hypocalcaemia (less than 2.0mmol/L) and patient is experiencing mild hypocalcaemic symptoms, a rescue dose of intravenous calcium gluconate (3g of intravenous calcium gluconate infusion over 4 hours) will be given as per current unit protocol. After completion of the rescue dose of calcium infusion, the serum calcium level will be repeated and further action will be taken based on the post-correction serum calcium level.

However, if the patient developed severe hypocalcaemia symptoms such as carpo-pedal spasm, bronchospasm/laryngospasm or cardiac manifestation, then an immediate biochemical investigation (corrected serum calcium level) will be obtained and an immediate rescue dose of intravenous calcium gluconate will be administered to the patient before the result are available. According to current unit protocol, if a patient developed severe hypocalcaemia symptoms, an immediate intravenous calcium slow bolus (1g of calcium gluconate) will be given over 20 minutes. This will be followed by intravenous calcium infusion (3g of intravenous calcium gluconate infusion over 4 hours) after biochemical confirmation of hypocalcaemia. After completion of the slow calcium bolus and calcium infusion, serum calcium levels will be repeated and further action will be determined based on the post-correction serum calcium level. The management of hypocalcaemic patients can be referred to **Appendix 3**. Both groups of patients will be followed-up until 48 hour post-operation. In the event of an emergency and there is a need to break the code, the clinician in charge of the patient will contact the principal investigator immediately to facilitate the rescue process.

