Data recorded will be analysed using SPSS Statistics Version 25. Continuous data will be expressed as Mean \pm standard deviation unless otherwise stated. Paired T- test was used for comparison of paired samples. The students's T- test was used for comparison of continuous variables between different groups. Chi-square test will be used for categorical data analysis. A value of $P < 0.05$ will be considered statistically significant. The data collected will be analysed using an per-protocol analysis.

[figure not shown]
Risk and Benefit to Study Participants

The dose and infusion rate of calcium used in this study is within the safety limits proposed by the World Health Organization (WHO). The adverse effects of calcium infusion are rare and may range from mild to severe. Common adverse effects including nausea, vomiting, hypertension, flushing and local inflammation over the infusion site. Severe adverse effects such as heart block and slow heart rate may occur but are extremely rare with this regime and dosage of calcium infusion. All study participants will be placed on cardiac monitoring and administration will be discontinued if adverse effects supervene. None of the patients in the endocrine surgery unit, UMMC experienced

any adverse effect after receiving intravenous calcium gluconate in the year 2018 and 2019. Therefore, there is very minimal risk for subjects who choose to participate in this study.

In the other hand, this study does not present any direct benefit to the participants who involved in this study. However, information obtained from this study will help to formulate a better treatment protocol/plan to reduce and prevent incidences of hypocalcaemia after total thyroidectomy.

Flow Chart

Ethical Consideration of Study

This study will be conducted in compliance with ethical principles outlined in the Declaration of

Helsinki and Malaysian Good Clinical Practice Guideline.

Informed Consent

Eligible patients will be identified during clinic visits. Information regarding the study will be given and explained to them during clinic visit. They will be allowed to take the patient information sheet home and consult with their family members. Informed consent will be obtained when they are admitted for surgery.

Privacy and Confidentiality

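### The primary investigator and an undefined group of assistants know each patient's arm, and the protocol does not separate them from recruitment or symptom assessment

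*Protocol*

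**What the plan says.** All of this is in the Protocol, mostly under Study Type and Design.

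- **Label:** "This is a single centre, double blinded and prospective randomized controlled trial".
- **Who is blind:** "Both the surgeon and patient will not be aware of the randomization arm of any particular patient".
- **Who is not:** "Only the primary investigator and assistants will be aware of the randomization of a patient". The number of assistants and their tasks are not given.
- **Recruitment:** patients "agree to participate in this study after explanation by the clinician and investigator in charge".
- **Timing:** allocation is "with the ratio of 1:1 during admission for surgery". Under Informed Consent, "Informed consent will be obtained when they are admitted for surgery".
- **Method:** "The method of randomization utilised will be random randomization". The main text names no sequence holder and no concealment device, and does not say who prepares the infusions.
- **Assessment:** "During blood taking and review, the patient will be assessed for symptoms of hypocalcaemia". The assessor is not named and is not said to be blind.
- **Code break:** in an emergency the treating clinician contacts the principal investigator.

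Under Study Endpoint, the outcome is corrected calcium over the first 48 hours. Length of hospital stay is the secondary objective.

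**The concern.** Blinding and concealment depend on keeping those who know the arm away from decisions that the arm could influence. Here the protocol states who holds the knowledge and leaves that group's duties open. The same people could explain the trial, obtain consent, review symptoms and take part in rescue decisions without departing from the text.

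Two things are at stake. If a recruiter can learn the next allocation, enrolment can be steered and the arms lose comparability at baseline. If a symptom assessor knows the arm, the extra tests and rescue treatment that follow from symptoms may differ between arms for reasons unrelated to the study infusion. Neither can be repaired in the analysis afterwards.

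**Working it through.** No sample size, target difference or event rate rests on this point, so there is no figure of the plan to reproduce. The check is to set the provisions side by side.

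1. **Knowledge of the arm.** The sentence on who is aware of the randomisation is a positive statement. The code-break route confirms that the principal investigator has the code (taking primary and principal investigator to be the same person).

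2. **Recruitment.** The recruiter is a clinician together with an investigator in charge. The text does not say whether this is the primary investigator or one of the assistants. Overlap is permitted, but not stated.

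3. **Concealment.** Consent and allocation fall in the same admission. Study Type and Design describes agreement to take part before it describes allocation, but gives no device that keeps the next assignment hidden until consent is complete.

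4. **Assessment.** Symptoms are reviewed at each blood sampling and graded mild or severe. The Literature Review shows how much judgement this needs. It lists tingling both as a complaint of low calcium and as a complaint after intravenous calcium, and it says Chvostek's sign is present in 10% of normal individuals. An assessor who knows the arm could read the same complaint differently in each arm.

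5. **From symptoms to outcomes.**
   - Mild symptoms lead to an immediate calcium test and, if the result is below 2.0 mmol/L, to rescue calcium.
   - Severe symptoms lead to a first rescue dose before the result is known.
   - Rescue changes later calcium. For example, rescue started after the 12-hour review comes before the 36- and 48-hour samples.
   - Under Current Protocol in UMMC, discharge at 48 hours requires absence of symptoms as well as normal calcium, so symptom judgement reaches length of stay.

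6. **Direction.** If symptoms are sought harder in the saline arm, more saline patients may receive rescue calcium. Their later calcium rises and the difference shrinks. If symptoms are discounted in the calcium arm, those patients may have fewer extra tests and earlier discharge, which favours the intervention. Both are possible.

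7. **Pilot split.** Sample Size puts 10 pilot patients into 5 per arm. Under simple randomisation with equal probabilities, the chance of an exact 5:5 split is C(10,5)/2^10 = 252/1024 = 0.246. The planned split therefore implies a restricted scheme, which the main text does not name.

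**The case against.** The strongest reply is that the outcome is well protected. Corrected calcium is a laboratory value taken at scheduled times. Numbness and tingling are reported by a patient who is blind. Rescue for mild symptoms also needs a calcium result below 2.0 mmol/L, the follow-on infusion after severe symptoms needs biochemical confirmation, and discharge needs a normal calcium after a routine stay of at least 48 hours. The code-break rule makes sense only if the treating clinician is blind. Appendix 2, cited for randomisation, and the flow chart are not in the text at hand and may add detail.

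Much of this stands. Direct bias on the laboratory endpoint should be small, and the biochemical conditions limit how far symptom judgement can carry. They do not close the route. The mild-symptom test is itself triggered by symptom review, the first dose for severe symptoms precedes the result, and the assessor may be someone other than the blinded surgeon. An appendix could add concealment, but it would not undo the main text's statement of who knows the arm.

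A reader might also infer that the double-blind label is false. The document does not support that, because blinding surgeon and patient is one usual meaning of the term. Nor does it show that recruiters will see the next allocation; it only fails to prevent it.

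**Conclusion.** The point holds as a defect in the allocation of roles. The protocol gives the code to the primary investigator and an open-ended group of assistants, and the text at hand keeps none of them from recruitment, consent or symptom assessment. The exposure lies in symptom grading, unscheduled tests, rescue calcium and its effect on later values, and length of stay. It lies much less in the laboratory measurement itself.

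The size cannot be computed. The protocol states no target effect and defers its sample size to the pilot, so there is nothing to scale a possible bias against. A reader might infer that the bias must favour calcium gluconate, but the rescue route can equally pull the arms together. A reader might also infer that simple randomisation would break the 1:1 ratio. It would not, because equal probabilities satisfy that ratio; only the exact 5 per arm in the pilot calls for restriction.

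The conclusion assumes that the appendices and flow chart, which are not at hand, contain no separation of roles. If they do, the main text should be brought into line with them.

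**What to change.** Rewrite the randomisation paragraph under Study Type and Design so that:

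- one existing person, for example the pharmacist or the assistant who prepares the infusions, is the only one who knows the allocation;
- that person holds a computer-generated list with randomly varying block sizes, with the pilot's blocks summing to 10 (for example 4 + 6) so that 5 per arm is met;
- an assignment is made only after consent is recorded;
- that person prepares identical coded infusions and takes no part in recruitment, symptom assessment, or rescue and discharge decisions;
- the primary investigator and all other assistants are blinded;
- sealed code-break envelopes are kept, so that the emergency contact still works without the primary investigator knowing every arm.

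State explicitly that recruiters and symptom assessors are blind. No dose or clinical rule changes. The cost is one revised paragraph and a reassignment of existing staff, with the small drawback that the preparer cannot do other trial tasks. It must be in place before the first patient, pilot included, is randomised.

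### Allocating at admission makes four-gland removal an avoidable exclusion after randomisation; releasing the allocation after skin closure would prevent it

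*Protocol*

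**What the plan says.** The order of events comes mainly from the Protocol, Methodology, Study Type and Design. Patients are allocated "with the ratio of 1:1 during admission for surgery". The text then turns to the pre-operative blood tests and the operation, and adds a rule for an intra-operative event, the accidental loss of every parathyroid gland. Where that happens, the rule reads: "these patients will be excluded from the study as this will definitely affect their serum calcium levels post-surgery". The study infusion, calcium or saline, is given only after the operation, within 4 hours of skin closure.

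The same section blinds the surgeon and the patient, but states: "Only the primary investigator and assistants will be aware of the randomization of a patient". It does not say who confirms four-gland removal or who decides the exclusion. Data Analysis names a per-protocol analysis and no other.

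On baseline calcium, Study Type and Design says: "Before surgery, baseline serum calcium, magnesium and i-PTH will be obtained". Under Current Protocol in UMMC, patients "will have their baseline serum calcium and i-PTH levels checked one day before surgery". A pre-operative calcium outside 2.2-2.6 mmol/L appears under Exclusion Criteria. Consent is taken at admission (Informed Consent).

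**The concern.** A patient who loses all four glands has already been allocated and is then taken out of the study altogether, not merely left without the infusion. The reason given is the expected effect on serum calcium, and Study Endpoint names corrected calcium over the first 48 hours. The exclusion is therefore made after randomisation and on a strong predictor of the outcome.

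Such an exclusion is harmless if it falls equally on both arms. It distorts the comparison if it falls unequally, either by chance in small groups or because someone who knows the arm influences which patients count as excluded. The protocol leaves the second route open, and its only named analysis does not bring excluded patients back. The exposure is also unnecessary, since no step before skin closure depends on the arm.

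**Working it through.** **Sequence.** Placed in order, the steps are:

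1. Consent at admission (Informed Consent).
2. Allocation 1:1 during admission (Study Type and Design).
3. Baseline calcium before surgery, one day before under unit routine. Its order relative to step 2 is not stated.
4. Operation, at which four-gland removal becomes known and leads to exclusion.
5. Skin closure, then the infusion within 4 hours. This is the first step that needs the arm.

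Four-gland exclusion (step 4) follows allocation (step 2). Moving allocation to between steps 4 and 5 makes it an exclusion before randomisation, so the number of randomised patients lost for this reason becomes 0 by construction. The same patients are eligible either way.

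**Size.** The protocol states no exclusion rate, final sample size or power, so there is no figure to reproduce. The following is illustration only.

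*Pilot.* Sample Size gives 10 patients, 5 per arm, whose mean and standard deviation set the trial size. One exclusion removes 1/5 = 20% of an arm and cuts the degrees of freedom of a pooled standard deviation from 5 + 5 − 2 = 8 to 4 + 5 − 2 = 7.

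*Uneven exclusion.* Suppose k more patients are excluded from one arm than from the other, and each would have become hypocalcaemic. With n the arm size including them and p the rate among those kept, the rate with everyone counted is (p(n − k) + k)/n. The observed rate is therefore too low by k(1 − p)/n. The rates are the unit's own for symptomatic hypocalcaemia within 48 hours, 23% in 2019 and 40% in 2018 (Introduction). The values of n and k are assumed.

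| k | n per arm | p = 23% | p = 40% |
|---|---|---|---|
| 1 | 20 | 0.77/20 = 3.9 points | 0.60/20 = 3.0 points |
| 1 | 50 | 0.77/50 = 1.5 points | 0.60/50 = 1.2 points |
| 1 | 100 | 0.77/100 = 0.8 points | 0.60/100 = 0.6 points |
| 3 | 20 | 2.31/20 = 11.6 points | 1.80/20 = 9.0 points |

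*Lost numbers.* To keep 100 evaluable patients when a share d is excluded after allocation, 100/(1 − d) must be randomised. Rounded up, this is 102, 103, 106 or 112 for d = 1%, 2%, 5% or 10%. These shares are also assumptions.

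**The case against.** The strongest reply is that four-gland removal precedes any study infusion and happens in the hands of a surgeon who does not know the arm. Treatment cannot cause it and allocation cannot steer the operation, so the exclusion is balanced in expectation. That it predicts outcome does not by itself create bias; unequal exclusion would. This stands. A reader might infer that the exclusion in itself breaks the randomised comparison, and the document does not support that. What remains is chance imbalance in small groups and the possibility of influence by staff who know the arm. The protocol does not give those staff the decision, but it does not keep the decision from them either.

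A reader might also infer that randomised patients are removed for an out-of-range baseline calcium. The protocol does not say so. It introduces its criteria with "There are several inclusion and exclusion criteria for recruitment into this study", which places them ahead of allocation, and calcium is one of them. The blood draw is mentioned after allocation, but sentence order does not fix the sequence. The supportable statement is narrower: the protocol does not require the calcium result before allocation.

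Nor does the no-replacement rule under Withdrawal Criteria show that these losses go unreplaced. It concerns subjects who choose to leave; replacement of patients excluded at operation is not addressed.

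Finally, Appendix 2, to which the allocation sentence refers, and the flow chart are not available in the text reviewed, and either may fix the order more closely. Read literally, allocation during admission could cover the whole stay, but the section describes it ahead of the baseline tests and the operation, so allocation before surgery is the natural reading.

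**Conclusion.** The point holds for four-gland removal. The protocol randomises before surgery and then excludes on an intra-operative event linked to its endpoint, when the allocation is not needed until after skin closure. The comparison is exposed to selective exclusion by unblinded staff and to chance imbalance, with a per-protocol analysis as the only one named. Bias is possible but not shown, and on average the event should balance.

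Its size cannot be fixed from the document. In the pilot a single exclusion is 20% of an arm. In the main trial one excess exclusion shifts an arm's rate by 0.6 to 3.9 points over the assumed range of 20 to 100 per arm, if that patient would have become hypocalcaemic. For baseline calcium, the finding is only that the order of result and allocation is left open. The conclusion rests on reading allocation as taking place before surgery. The matter is worth correcting because the correction is cheap, not because the design is invalid as it stands.

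**What to change.** In Study Type and Design, keep consent at admission and move the release of the allocation. Suggested wording:

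> The allocation is released only after skin closure, once the eligibility criteria, including a baseline calcium within the stated range, have been confirmed and the surgeon has recorded that not all four parathyroid glands were removed. All patients allocated from that point are analysed in the arm to which they were allocated.

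Amend Data Analysis to match. If allocation at admission has to stay, the blinded surgeon should confirm and record four-gland removal, and these exclusions should be reported by arm.

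The main change costs a revision of wording and a later allocation step, with no extra patients, tests or staff. Its small downside is that the allocated infusion must be prepared within the existing 4-hour window.
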